1. BACKGROUND

1.1 Epidemiology and burden of the condition

Care of the critically ill typically occurs in the intensive care unit (ICU), although it may commence elsewhere, such as the operating theatre or emergency department. If a patient cannot breathe adequately, they may be assisted by mechanical ventilation. This involves placing a tube into the trachea (endotracheal tube (ETT)), which connects to a ventilator. This system ‘takes over’ breathing for the patient. In the UK, over 60,000 adults receive invasive ventilation each year[1], with most of these surviving to leave hospital (66%)[2]. Mechanical ventilation is known to be associated with some clinically important unwanted effects; one is Ventilator-Associated Pneumonia (VAP). Patients who develop VAP have a protracted ICU stay and worse outcome. In addition to the personal cost and risk for each patient, there are significant healthcare costs associated with a protracted stay on ICU, with each day of care costing around £1500. [3, 4].

VAP is the most common Hospital Acquired Infection (HAI) in ICUs occurring in ~30% of mechanically ventilated patients [5-8]. This increased to 45% during the COVID-19 pandemic.[9] A new class of endotracheal tube aimed at providing advanced airway protection may significantly reduce the incidence of VAP (pneumonia occurring >48 hours after intubation)[10] and in turn the length of mechanical ventilation and stay on ICU. Consequently, reducing VAP incidence is important to patients, clinicians, and policy makers.

The National Institute for Health and Care Excellence (NICE) produced medical technologies guidance 48, (April 2020) [11], highlighting the potential for a new ETT, an advanced airway protection device, to prevent Ventilator Associated Pneumonia[11]. However, the current evidence base is not strong enough for formal NICE approval. Therefore, NICE have recommended definitive research to assess the clinical and cost effectiveness of such advanced airway devices in NHS critical care. NICE have identified the PneuX system as the only current example of an advanced airways protection system, that has the best current evidence for the potential to reduce ventilator associated pneumonia and in turn reduce length of time on a ventilator.

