2.3 Aims and objectives

Objectives:

- (1) Conduct an internal pilot study to confirm the feasibility of a large-scale multicentre trial.
- (2) To conduct a UK-wide multi-centre, open-label, pragmatic, individually randomised, parallel group trial and economic evaluation to determine the clinical and cost effectiveness of an advanced airways protection device versus conventional endotracheal tubes (with and without basic subglottic manual suction and standard cuff) in patients with respiratory failure requiring mechanical ventilation. The outcomes are duration of mechanical ventilation, survival, ICU, and hospital stay outcomes and health-related quality of life.
- (3) Estimate, in an integrated economic evaluation, the cost-effectiveness of an advanced airways protection device versus the conventional endotracheal tubes.

Justification of outcomes

We have worked with patients, the public, researchers and clinicians to determine both our primary and secondary outcomes. This clinical effectiveness trial comprises key core outcomes from the Core Outcomes in Ventilation Trials (COVent) core outcome set and NICE guidelines for ventilation trials and NICE guidelines [5, 12, 13].

Primary effectiveness outcome

The primary variable (outcome) of interest is the duration of mechanical ventilation as measured from time from randomisation to first successful unassisted breathing, measured in days. This outcome is one of the 'COVenT' core outcomes for trials of interventions intended to modify the duration of mechanical ventilation[14]. To clarify:

- Unassisted breathing is defined as no inspiratory support or extracorporeal lung support
- Success is defined as maintaining unassisted breathing at 48 hours.
- Duration includes time receiving extracorporeal lung support, invasive mechanical ventilation and non-invasive ventilation delivering volume or pressure support ventilation.
- Duration excludes time receiving high-flow oxygen therapy and continuous positive airway pressure.
- Patients with a tracheostomy in situ may still achieve successful unassisted breathing.

Secondary outcomes - refer to CoReCCT master protocol for core clinical outcome set.

Effectiveness

- *Duration of endotracheal intubation*: time from randomisation to endotracheal extubation (in hours).
- Ventilator Associated Pneumonia (VAP): Diagnosed by treating clinician with commencement of antibiotics [16] from randomisation up to ICU discharge.

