- Hospital Acquired pneumonia (HAP) following extubation- clinician diagnosis and commencement of antibiotics from randomisation up to ICU discharge.

Safety Outcome Measures

Reportable safety events are described in section 7 of the CoReCCT Master Protocol.

Adverse event rates, including device-related

Adverse event rates related to endotracheal tube intubation within 1 hour of intubation, or tube change if allocated to intervention arm:

- *Traumatic insertion, bleeding*
- *Injury to the throat or trachea*
- *Dental damage*
- *Failed intubation*
- *Aspiration during intubation*
- *Pneumothorax*
- *Obstruction or kinking of the endotracheal tube*
- *Cuff leak*
- *Unintentional extubation*

Adverse event rates related to endotracheal tube intubation after one hour of intubation, or tube change if allocated to intervention arm, up to ICU discharge:

- *Tracheal stenosis*
- *Vocal cord injury / paralysis / Arytenoid dislocation*
- *Hoarse voice / voice changes*
- *Sinusitis*
- *Laryngo-tracheal stenosis*
- *Tracheomalacia*
- *Obstructive fibrinous tracheal pseudo membrane*
- *Pressure injuries related to tube securing or pressure from tracheal tube*

- *Tracheo-oesophageal fistula*
- *C-spine and spinal cord injuries due to intubation*

Patient reported and health-economics outcomes:

- Costs associated with use of NHS & personal social services (PSS) resources arising during hospital stay and after hospital discharge; personal expenditures (out-of-pocket costs) incurred by patients after hospital discharge. (also see section Health Economic Evaluation).
- Health-related quality of life using a widely used and recommended preference-based quality of life instrument (EQ-5D-5L) collected at 2 and 6 months.

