Performance and detection bias (unblinded study): The nature of the trial intervention precludes masking of patients or care providers following randomisation. We will mitigate against potential bias in the absence of blinding, by using an objective measurable primary outcome (duration of mechanical ventilation (days)), and collecting data on intubation and readiness to extubate, and reasons why this might not occur as planned, to confirm consistency across randomised groups and assess performance bias on the part of treating clinicians. Intensive care clinical charts provide contemporaneous, hour by hour records of the patient's physiology and current treatments. Source verification (from clinical records) and hospital computer records will be used to minimise the risk of reporting bias. The main clinical and resource utilisation outcomes of this trial (e.g., ventilation status (hourly); death; level 2/3 care; adverse events, antibiotic uses) are recorded contemporaneously on patient clinical records and hospital information systems. This will enable outcomes to be verified by both site staff and the coordinating centre. It will also not be possible to directly blind the WCTU (Warwick Clinical Trials Unit) trial team to treatment allocation, as this information will be collected on the patient clinical record forms and will be necessary to monitor and manage protocol deviations and compliance/adherence. However, the team will have some blinding regards the randomised intervention, whilst collecting the follow-up outcome data. At the pilot stages, we will assess the patient baseline characteristics at site level, to identify any outliers which may have resulted due to our inability to blind the trial. The trial statistician, who has no role in decision-making with regards the conduct of the trial, will be unblinded and this will also facilitate linkage with the DMC.

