3. METHODS AND ASSESSMENTS

3.1 Schedule of delivery of intervention and data collection

Table 1 summarises the trial schedule of events and timing of data collection.

Table 2 Trial assessments

	Timing of assessment				
	Baseline	Hospital stay	Hospital discharge	2 months	6 months
Eligibility assessment	✓				
Deferred consent ^a / Consent/ consultee ^b agreement	✓	✓*			
Baseline data collection	✓				
Randomisation	✓				
Intervention	✓	✓			
Critical care/ hospital stay data			✓		
Survival status		✓	✓	✓	✓
Quality of life (EQ-5D-5L) and health resource use questionnaire				✓	✓
Safety reporting		✓	✓		
^a not in Scotland ^b in Scotland referred to as welfare guardian/nearest relative *- only applicable if consultee agreement/deferred consent used as basis for initial enrolment					

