4.1 Pre-Specified Complications

As per the CoReCCT Safety Reporting Flowchart, adverse events that 1) occur at sites between randomisation and hospital discharge and 2) are not present on the CoReCCT Exemption List, must be reviewed for their presence on the PROTECT Airways Pre-Specified Complications List as given below (Table 2)

The duration of mechanical ventilation from randomisation to liberation is the primary objective of this study. Therefore, any clinically relevant intubation and mechanical ventilation related event occurring from the time of randomisation until ICU discharge will be recorded as pre-defined trial outcomes (see as listed in Safety Outcomes Section 2.2 above and SAE reporting exemptions below).

Table 3 Pre-Specified Complications List (safety outcomes)

Pre-Specified Complications List (safety outcomes)

Adverse event rates related to endotracheal tube intubation within one hour of intubation or tube change if allocated to intervention arm:

- *Traumatic insertion, bleeding*
- *Injury to the throat or trachea*
- *Dental damage*
- *Failed intubation*
- *Aspiration during intubation*
- *Pneumothorax*
- *Obstruction or kinking of the endotracheal tube*
- *Cuff leak*

- *Unintentional extubation*

Adverse event rates related to endotracheal tube intubation after one hour of intubation, or tube change if allocated to intervention arm, up to ICU discharge

- *Tracheal stenosis*
- *Vocal cord injury / paralysis / arytenoid dislocation*
- *Hoarse voice / voice changes*
- *Sinusitis*
- *Laryngo-tracheal stenosis*
- *Tracheomalacia*
- *Obstructive fibrinous tracheal pseudo membrane*
- *Pressure injuries related to tube securing or pressure from tracheal tube.*
- *Tracheo-oesophageal fistula*

- *C-spine and spinal cord injuries due to intubation*

As per the CoReCCT Safety Reporting Flowchart, if the event is present on the Pre-Specified Complications List, the event must be recorded on the appropriate CRF as an outcome and does not need to be reported as an SAE. If the event is not on the list, it must be assessed for seriousness and the remainder of the flowchart should be followed to determine next steps.

The target population for the trial is the broad group of patients that require intubation and mechanical ventilation. These patients are the sickest in the hospital and are at risk of physiological deterioration, including the need for increased organ support, and death. These events are captured as clinical outcomes.

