use the inverse probability weighted analysis method to assess the treatment effect, having taken account of these events [35]. We will also assess the impact of crossovers on the statistical power of the study: due to the contamination effect in patients who crossover from one intervention to another, there is likely to be a reduction in the trial power. We will examine the loss of power, using power curves and different degrees of crossover, pivoted around the observed crossover rates, and assess this at the end of the pilot study as well as presenting these to the DMC at each 6-monthly analysis [36]. For ICE 3, we will use compliers average causal effect (CACE) analyses [37].

Secondary outcome analysis

In general, continuous baseline and outcome data will be summarised with descriptive statistics, including n, mean, standard deviation, median, interquartile range, and n of missing data. Mixed-effects linear regression models will be used to estimate mean treatment differences (95% CI). Categorical baseline and outcome data will be summarised with frequency counts and percentages and mixed-effects logistic regression models will be used to estimate the difference in binary outcomes between treatment groups, with odds ratios and 95% CIs reported.

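### Hospital-acquired pneumonia after extubation is counted only to ICU discharge, so pneumonia arising on the ward falls outside both pneumonia outcomes

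*Protocol*

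**What the plan says.** Section 2.3 lists among the secondary outcomes "Hospital Acquired pneumonia (HAP) following extubation", defined by "clinician diagnosis and commencement of antibiotics from randomisation up to ICU discharge". VAP, the item before it, also rests on the treating clinician's diagnosis with antibiotics started, and it has the same start and end. Nothing in the protocol extends either outcome to the ward.

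Other parts of the protocol bear on this:

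- Section 1.1 expects the device to reduce VAP and "in turn the length of mechanical ventilation and stay on ICU".
- Section 2.11 states that staff and patients cannot be blinded.
- Section 6.2.2 says that "mixed-effects logistic regression models will be used to estimate the difference in binary outcomes between treatment groups". It mentions no time at risk for these outcomes.
- Table 2 (section 3.1) places "Critical care/ hospital stay data" at hospital discharge.
- Section 4.1 reviews adverse events that "occur at sites between randomisation and hospital discharge".
- Section 2.10 says that the main clinical outcomes, antibiotic use among them, "are recorded contemporaneously on patient clinical records and hospital information systems".

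**The concern.** The window does not fit the outcome's name at either end. It opens at randomisation, when a post-extubation event cannot yet occur, and it closes at ICU discharge, when the patient is still in hospital. The first is loose wording. The second loses cases.

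The device is tested because it may prevent pneumonia. If patients come off the ventilator sooner and some then develop pneumonia on the ward, the two pneumonia outcomes would show fewer cases whether pneumonia had been prevented or had only come later.

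A second, weaker worry is that ICU discharge follows randomisation and is decided by clinicians who know the allocation. If the interval from extubation to ICU discharge differs by arm, a comparison of proportions mixes pneumonia risk with length of observation.

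**Working it through.** **What the wording implies.** Take a patient extubated on day 6, moved to the ward on day 7 and treated for pneumonia on day 8. HAP does not count, because ICU discharge came first. VAP does not count, for the same reason. This needs no assumption.

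**The plan's own figure.** The protocol gives none for HAP. Its sample size can be reproduced and does not involve HAP. The adjusted hazard ratio is 1.2^0.901 = 1.1785. With 90% power and a two-sided 5% level (two-sided is assumed), the Freedman formula gives 1565 events, and 1565/(1 − 0.256 − 0.03) = 2192 against the stated 2194.

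**Share of cases missed (all inputs assumed).** Let h be the daily hazard in ICU after extubation, W the days from extubation to ICU discharge, D the ward days, and r the ward hazard relative to ICU. Then:

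- probability counted = 1 − exp(−hW)
- probability in hospital = 1 − exp(−hW − hrD)
- share missed = 1 − counted / in hospital

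With h = 1–2% per day, W = 3–5, D = 5–10 and r = 0.5–1:

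- Highest (h = 0.01, W = 3, D = 10, r = 1): 1 − 0.0296/0.1219 = 76%.
- Lowest (h = 0.02, W = 5, D = 5, r = 0.5): 1 − 0.0952/0.1393 = 32%.

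In time rather than cases, assuming 1–3 ICU days after extubation and 7–14 ward days, the window covers 1/(1 + 14) = 7% to 3/(3 + 7) = 30% of the time at risk in hospital.

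**Effect of an unequal window, with no true effect on daily risk (all inputs assumed).** Let the control window be W = 3–5 days and the device window W − d, with h = 1–3% per day. For h = 0.01, W = 3, d = 1 the proportions are 0.0296 and 0.0198, an odds ratio of 0.66. Over the grid:

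| Device window shorter by | Odds ratio | Chance of a significant result for the device, 1097 per arm |
|---|---|---|
| 0.5 day | 0.83 to 0.90 | 8% to 22% |
| 1 day | 0.66 to 0.80 | 19% to 71% |
| 0 (equal windows) | 1 | no excess over the nominal level |

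The last column treats all 1097 patients per arm as extubated, so it overstates the chance to some degree. If the device arm has the longer window, exchanging the arms gives the reciprocals: about 1.11 to 1.20 for 0.5 day and 1.25 to 1.52 for 1 day, against the device.

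**The case against.** A reader might infer that the device is bound to look better on HAP because it is expected to shorten ICU stay. The protocol does not support that. Section 1.1 links a shorter ICU stay to less VAP and shorter ventilation, whereas the HAP window runs from extubation to ICU discharge. If both come forward by a day, the window is unchanged. If extubation comes forward and ICU discharge does not, the device arm is at risk for longer. A difference by arm is possible but not implied.

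A reader might also infer that the cost of ward pneumonia is lost. It is not. Sections 2.3 and 6.5 cost the hospital stay, including ward stay and pulmonary complications, over 6 months, and QALYs run to 6 months.

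Four further objections deserve weight:

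- Stopping at ICU discharge is consistent across VAP, HAP and the late tube complications, and may be a deliberate limit on site burden. That explains the choice but does not bring ward cases into an outcome named hospital-acquired.
- Hospital discharge is also a post-randomisation event. This stands, and is why a cap at a fixed day is preferable.
- The CoReCCT master protocol is not at hand, and ward pneumonia may be recorded under it. This stands: ward cases are missing from the HAP outcome, not demonstrably from the trial's data.
- An overlap of VAP and HAP in ventilated tracheostomy patients is mainly a matter of how extubation is read. Section 2.3 does foresee tracheostomy ("Patients with a tracheostomy in situ may still achieve successful unassisted breathing"), but that line concerns unassisted breathing. One classification sentence is enough.

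**Conclusion.** The point holds as a limit of one secondary outcome. As defined, HAP excludes ward-onset pneumonia, VAP does not pick it up, and the two together cannot separate prevention from later onset. That follows from the text alone.

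Its size cannot be taken from the protocol. The 32% to 76% of cases missed rests wholly on the assumed hazards and lengths of stay. Differential time at risk is a possibility of unknown sign and size, and nil if the post-extubation ICU interval is equal in both arms.

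The primary outcome, the sample size of 2194 and the main economic analysis are untouched. This is an inexpensive improvement, not a threat to the trial's main conclusion.

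**What to change.** In section 2.3:

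- Count HAP from extubation to hospital discharge, using the hospital-discharge data collection already in Table 2. Preferably cap it at a fixed day after randomisation, the same in both arms. The protocol offers no basis for a particular day, so the team should choose and state it.
- Beside the separate outcomes, report VAP or HAP combined, from randomisation over the same horizon, with death as a competing event. This starts both arms at the same point and does not depend on when extubation or ICU discharge occurs.
- State that each pneumonia episode is classified once: VAP if the patient is on invasive ventilation, including through a tracheostomy, and HAP otherwise.

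The cost is a change of outcome wording and an added CRF item at hospital discharge. The downside is small but real: staff at each site must check ward antibiotic and diagnosis records for the rest of the stay. The sample size does not change.

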2.5 Participant identification / Screening

Staff will identify potential participants in appropriate clinical areas, such as emergency departments, critical care units, acute wards, operating theatres. Potential processes for identifying patients include referrals, screening in clinical areas, or review of electronic health systems using appropriate queries. We will work with each participating site to support the development of strategies to optimise screening in their hospital.

Screening information will be entered on to a trial web application, hosted by Warwick Clinical Trials Unit (WCTU). This will capture anonymised data on the numbers of patients meeting inclusion criteria for the trial but not entered into the trial along with the reasons for non-enrolment. These data are important to understand the generalisability of the recruited patient population.

Screening of patients will involve reviewing personal identifiable information. This may be undertaken by a member of the patient's existing clinical care team, or by a member of the hospital research team, depending on local arrangements. Screening and eligibility assessment may be undertaken by any individual clinically competent to undertake that role, as determined by the principal investigator. It is anticipated that this process may be undertaken at any time of day or night, provided appropriately trained staff members are available.

Patients who need intubating, or who have been intubated within the last 24 hours prior to randomisation are eligible for the trial. Confirmation that all eligibility criteria are met will be entered on to the trial web application prior to the patient being randomised.

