2.8 Randomisation

2.8.1 Randomisation

A bespoke online randomisation system will be developed, by the WCTU programming team. The system will be based on a computerised algorithm using the minimisation method for randomising patients. The randomisation sequence will be created, stratified by hospital site, if the patient is intubated prior to randomisation and prior enrolment into the Awake Prone trial. Patients will be randomised, in a ratio of 1:1 to the advanced airways protection device or the standard of care endotracheal tube (with or without the basic subglottic suction/standard cuff). Randomisation can happen up to 24 hours after primary intubation. **If randomised to the intervention arm, this may necessitate a tube change. The tube change should occur within 24 hours of the patient initially being intubated.**

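### Four tube failures are listed only for the first hour, and tube changes only for the intervention arm, in conflict with the rule in 4.1 that runs to ICU discharge

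*Protocol*

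**What the plan says.** Protocol 2.3 (Safety Outcome Measures) gives two lists. The early list has nine items and is headed "Adverse event rates related to endotracheal tube intubation within 1 hour of intubation, or tube change if allocated to intervention arm". The late list has ten items, covering events "after one hour of intubation, or tube change if allocated to intervention arm, up to ICU discharge". Table 3 in 4.1 repeats both lists, the early one under "Adverse event rates related to endotracheal tube intubation within one hour of intubation or tube change if allocated to intervention arm".

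Four items appear in the early list only, in both places: pneumothorax, obstruction or kinking of the tube, cuff leak, and unintentional extubation.

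Section 4.1 also has a general rule. Clinically relevant events linked to intubation or ventilation, "occurring from the time of randomisation until ICU discharge will be recorded as pre-defined trial outcomes". The same sentence then points back to the safety outcome lists. Section 4.1 adds that an event on the list goes on the CRF as an outcome and is not reported as an SAE, and that an event not on the list is assessed for seriousness.

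On timing, 2.5 states: "Patients who need intubating, or who have been intubated within the last 24 hours prior to randomisation are eligible for the trial". Section 2.8.1 states: "Randomisation can happen up to 24 hours after primary intubation", and "If randomised to the intervention arm, this may necessitate a tube change". The allocation is stratified by, among other factors, "if the patient is intubated prior to randomisation".

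**The concern.** Section 2.9 distinguishes the device from the comparator mainly by its cuff, its continuous control of cuff pressure and its suction ports. Section 2.9 also foresees tube problems that call for a tube change, and one of the studies cited in 1.3 for safety and efficacy concerns unplanned extubation with this device. Cuff leak, blocked or kinked tubes and unintentional extubation are therefore events on which the arms could plausibly differ in either direction, over the whole time that the tube is in place. Listing them for the first hour only, while 4.1 speaks of the whole period to ICU discharge, leaves the definition of the outcome to each site.

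The arm condition on tube change is a second gap. Read literally, a tube change in a control patient opens no early window, even when it is made at a cross-over to the device, which 2.10 expects may happen.

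Staff know the allocation, so differences in how sites read the lists need not be equal between arms. This is a matter of data capture: events that the CRF does not ask for cannot be supplied by a later choice of analysis.

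**Working it through.** The protocol states no event rate, precision or power for these outcomes, so there is no figure of its own to reproduce. The sample size of 2194 rests on the primary outcome and is not touched.

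**1. A non-serious cuff leak on day 3, followed through the text.**

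| Reading | Route | Result |
|---|---|---|
| General rule in 4.1 governs | Falls between randomisation and ICU discharge | Recorded as a pre-defined outcome |
| One-hour heading governs; event is off the list | Assessed for seriousness; not serious | Not a listed outcome |
| Event is on the list by name, so exempt from SAE reporting, but outside the hour | CRF outcome limited to one hour | Left out |

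The general rule does not settle this, because it refers back to the same lists. Its cross-reference also names Section 2.2, the internal pilot, whereas the lists stand in 2.3.

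**2. Tube change by arm.** In the intervention arm a tube change opens a new first hour. In the control arm it does not. Re-intubation counts as intubation on a plain reading and so opens a window in either arm.

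**3. How short the early window is.** Input: median control ventilation 6 days (6.1), or 6 × 24 = 144 h.
- 1/144 = 0.69% of the median; at a 5-day median, 1/120 = 0.83%.
- With the protocol's Weibull shape of 0.901, the scale is 144/(ln 2)^(1/0.901) ≈ 216 h and the mean is 216 × Γ(1 + 1/0.901) ≈ 227 h. The first hour then holds about 0.44% of expected ventilated time, or 0.53% at a 5-day median.

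These are shares of ventilated time. They would be shares of events only at a constant event rate, which the protocol does not give. Early clustering, plausible for insertion-related pneumothorax, would raise the first-hour share. Ventilation as defined in 2.3 also includes non-invasive support, so it is not the same as tube time.

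**4. Early-window time after randomisation, by arm.** Assumptions, none stated in the protocol: the delay from intubation to randomisation is uniform over 0 to 24 h; every already-intubated intervention patient has a tube change; controls have no re-intubation; *s* is the share already intubated.
- Already-intubated controls whose first hour has closed by randomisation: 23/24 = 96%.
- Mean window left for already-intubated controls: (1/24) × 0.5 h = 0.021 h.
- Control window per patient: (1 − s) × 1 + s × 0.021 h. Intervention window: 1 h.
- Intervention-to-control ratio: s = 10%, 1/0.902 = 1.11; s = 50%, 1/0.510 = 1.96; s = 90%, 1/0.119 = 8.42.

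This ratio describes exposure to a first hour. Most of it arises because allocation to the device can require an exchange. A common definition would leave it largely in place and would add only the control tube changes that are not counted now.

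**The case against.** The best defence is that the protocol already casts a wider net. The 4.1 rule runs to ICU discharge, 2.3 has a broad line on adverse events including device-related ones with no hour limit, and 2.10 notes that adverse events are charted as they happen. Unlisted serious events go to SAE assessment. Section 7 of the master protocol holds the reporting flowchart and may capture more. Ten late tube-injury outcomes, among them stenosis, fistula and pressure injury, run to ICU discharge in both arms.

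All of this stands, and it rules out several stronger readings that a reader might infer:
- *That nearly all device failures are missed.* The 4.1 rule and the SAE route contradict this, and a figure such as over 99% would need a constant event rate that the protocol does not support.
- *That already-intubated controls can never have an early event.* A control randomised within the hour, or re-intubated later (2.9 provides for re-intubation), can have one.
- *That counting exchange harm in one arm is bias.* The exchange follows from allocation. Under the treatment-policy approach of 6.2.2 its harms are an effect of the strategy.
- *That no safety difference could be shown or excluded.* The late list, SAEs and mortality remain.

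The defence does not remove the conflict itself. The wide rule points to the narrow lists, the broad line in 2.3 is not defined further, and charted events reach the comparison only if the CRF asks for them.

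**Conclusion.** The point holds as an inconsistency in outcome definition that should be corrected. The one-hour limit on four tube events, and the arm condition on tube change, disagree with the 4.1 rule. As written, later non-serious failures of the tube, and early complications of control-arm tube changes, have no clearly listed and comparable outcome. The size in events cannot be given, since the protocol states no rates. The early window covers about 0.4% to 0.8% of ventilated time, depending on the median and on whether the median or the Weibull mean is the base.

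The difference in early-window time between arms is confined largely to patients intubated before randomisation. That share is not stated, but prior intubation is a stratification factor, so it can be examined directly. The conclusion rests on this protocol alone; the master protocol could narrow the gap.

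**What to change.** Reconcile the lists with the 4.1 rule, in both 2.3 and Table 3:
- Add cuff leak, obstruction or kinking, unintentional extubation and pneumothorax to the after-one-hour list, up to ICU discharge.
- Define the early window in both arms as within one hour of any intubation or tube change after randomisation, whatever the allocation. The late list then covers the remaining time from randomisation to ICU discharge.
- Correct the cross-reference in 4.1 to 2.3.
- Report early events by the existing stratification factor (intubated before randomisation or not), and interpret any excess of exchange-related events in already-intubated intervention patients as an effect of the allocated strategy.

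The cost is a few more CRF fields and a little more data entry. Treatment and sample size do not change.
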